3 DATA ANALYSIS CONSIDERATIONS

3.1 General presentation of summaries and analyses

Statistical analysis and generation of tables, figures, study participants data listings, and statistical output will be performed using SAS Version 9.4 or higher. All tables and listings will use Courier New font size 9.

Descriptive statistics will be displayed to provide an overview of the study results. For continuous variables, descriptive statistics will include number of study participants with available measurements (n), mean, standard deviation (SD), median, minimum, and maximum.

For PRO continuous variables, descriptive statistics will also include variable score, absolute and percentage changes from baseline, Q1 and Q3, 10th, and 90th percentiles.

If no participants have data at a given time point, then only n=0 will be presented. The other descriptive statistics will be left blank. If $n < 3$ then the n, minimum, and maximum only will be presented. The other descriptive statistics will be left blank. If $n = 3$ n, mean, median, minimum and maximum will be presented only. The other descriptive statistics will be left blank.

For categorical variables, the number and percentage of study participants in each category will be presented. Unless otherwise noted, the denominator for percentages will be based on the number of study participants included in the respective analysis set. Study participants with missing data will be accounted for using the following approaches:

- For summaries of demographics and Baseline characteristics: percentages will be based on all study participants in the analysis set and a “Missing” category (corresponding to study participants with missing data for the variable being summarized) will be included as the last row in the list of categories being summarized.
- For summaries of efficacy and safety endpoints, unless otherwise specified: percentages will be based only on those study participants with observed data for the variable being summarized. As the denominator may be different from the number of study participants in the analysis set being considered, the denominator will be displayed in the table. The general format for displaying this will be “n/Nsub (%)”.

Percentages will be presented to 1 decimal place. If the percentage is 100%, a decimal will not be presented. If the count is 0, the percentage will not be presented. Typically, the % sign will be presented in the column header, but not with each individual value.

For the purpose of the tabulations the lower and upper confidence limits for the percentages will be truncated at 0 and 100% respectively. Confidence intervals (CIs) for the response rates in efficacy summaries based on nonresponder imputation (NRI) will be computed using the Wilson approximation.

For bimekizumab PK concentrations, summary statistics will include geometric mean, geometric coefficient of variation (CV), 95% CIs for geometric mean, arithmetic mean, SD, median, minimum, and maximum. All summaries of PK variables will be based on the observed values. No imputation will be used.

Decimal places for descriptive statistics will be subject to the following rules:

- “n” will be an integer

- Mean, SD, and median will use 1 additional decimal place compared to the original data
- CV [%] will be presented with 1 decimal place
- Minimum and maximum will have the same number of decimal places as the original value.

Derived variables in general will display the mean, SD, and median to 1 more decimal place than the variables used in the derivation. If the number of decimal places reported in the raw data is varied then use either the maximum raw number of reported decimal places or 3, whichever is the lowest, as a guide for the descriptive statistics.

When reporting individual values and descriptive statistics for PK concentration data, the following rules will apply with regard to rounding and precision:

- Individual values will be reported to the same level of precision as received from the bioanalytical laboratory
- Descriptive statistics will be reported to the same level of precision as the individual data for the minimum and maximum, and to 1 additional significant figure for the mean (arithmetic and geometric), median, SD, and 95% CI for the geometric mean
- The geometric coefficient of variances (geoCV) will be reported as a percentage to 1 decimal place

Statistical tests of efficacy variables will be presented as 2-sided p-values rounded to 3 decimal places. P-values less than 0.001 will be presented as “<0.001” and p-values greater than 0.999 will be presented as “>0.999.” Statistical comparisons will be 2-sided and will be performed at the 0.05 level of significance unless specified otherwise. The significance levels used as part of the multiple testing procedure are detailed in Section 4.5.

Per protocol, visit windows are ± 3 days from the date of first dose. The 20-week SFU Visit window is ± 7 days from the date of the final dose. All by-visit summaries will contain nominal (ie, scheduled) visits only. Unscheduled visits will not be mapped to scheduled visits except for assessments that occur within a 3-day time window of a scheduled visit. In that case, the assessment will be mapped to the corresponding scheduled visit and will be used for the analysis. This will only occur for selected vendor data. The only exception to this rule is for unscheduled assessments that occur up to 3 days after the Baseline visit. These unscheduled visits will remain as unscheduled as the Baseline assessment cannot be after the first dose of study drug administration. See Section 3.3 for more details on the definition of Baseline values.

A complete set of data listings containing all documented data as well as calculated data (eg, change from Baseline) will be generated.

3.2 General study level definitions

3.2.1 Relative day

The relative day will be included in different listings and will be calculated as follows:

- If the start (stop) date occurred on or after the first dose, but prior to the double-blind drug stop date, relative day is calculated as start (stop) date minus first dose date + 1

- If the start (stop) date occurred after the last dose of double-blind drug, the relative day to the most recent dose is calculated as start (stop) date minus most recent dose date. The relative day in this situation will be preceded by a '+'
- If the start (stop) date occurred before the first dose, the relative day is calculated as start (stop) date minus first dose date. The relative day in this situation will be preceded by a '-'.

For AEs, relative days for start and stop dates will be calculated as the number of days since the first injection of the medication. For non-treatment emergent AEs, relative day of onset will be negative if the event started and stopped before the first dose. Relative day will only be computed for fully completed dates and will be missing for partial dates.

Relative day will be calculated from first dose of IMP for all treatment groups, and additionally from first dose of bimekizumab for the Placebo/BKZ [REDACTED] arm.

3.2.2 Mapping of data from Premature End of Treatment visits

If the Premature end of treatment (PEOT) visit occurs at a scheduled visit as outlined in the schedule of assessments, then no mapping is necessary, and any early withdrawal assessments will correspond to that scheduled visit. The PEOT assessments that occur on a date after a scheduled visit will be assigned to the next scheduled site visit per the protocol following the last visit where assessments were available. This approach means that there is a chance that data will be mapped to a visit where a given assessment was not actually collected per the protocol schedule of assessments. Such data will not be summarized in by-visit tables (though it will be available in the listings).

The only exception to the above rule is for anti-bimekizumab antibody assessments, in which all PEOT assessments will be assigned to the next scheduled visit at which anti-bimekizumab antibodies are assessed. All by-visit summaries will contain nominal visits only. Unscheduled visits will not be mapped to scheduled visits. Note that based on the early withdrawal mapping conventions described above, a mapped PEOT visit is considered as observed at that visit and will be summarized as such in the tables.

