7 MEASUREMENTS OF TREATMENT COMPLIANCE

Due to the method of administration of the treatments, compliance will be examined in terms of completed injections.

Treatment compliance will be calculated as:

$$\frac{N_{actual}}{N_{expected}} \times 100\%$$

where N_{actual} is the total number of actual (completed) injections, and $N_{expected}$ is the total number of expected injections. In this study, dosing occurs [REDACTED] from Week 0 to Week 46, where 2 injections are administered at each given visit either with active dosing or placebo injection. It is expected that a participant should complete a total of 48 injections by the end of study. If a participant discontinues early, then the number of expected injections is based on the time of early discontinuation relative to the dosing visits. For example, if a participant discontinues after Week 8 visit and prior to Week 10 visit, the total number of expected injections will be 10.

A summary of percent treatment compliance categorized as <75% and ≥75% will be provided by treatment group for each study period (Initial Treatment Period for the RS, Maintenance Treatment Period for the MS, and the combined Initial and Maintenance Treatment Period for the AMS).

A by-participant listing of treatment compliance will be provided.

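### The SAP places an off-schedule premature-end-of-treatment visit by visit order with no date limit, so a late value can stand as the observed Week 16 HiSCR50 and a near-Week-16 value can be filed at a much earlier visit

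*SAP*

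**What the plan says.** SAP Section 3.2.2 distinguishes two situations.

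- A PEOT that coincides with a scheduled visit stays where it is: "If the Premature end of treatment (PEOT) visit occurs at a scheduled visit as outlined in the schedule of assessments, then no mapping is necessary".
- Any other PEOT "will be assigned to the next scheduled site visit per the protocol following the last visit where assessments were available".

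The section adds that "a mapped PEOT visit is considered as observed at that visit and will be summarized as such in the tables". Its only exception is for anti-bimekizumab antibodies, which go to the next visit at which they are assessed. It gives no target day, nearest-visit test or upper time limit for lesion counts or questionnaires.

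Three other places matter.

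- Section 3.1 states the protocol tolerance: "Per protocol, visit windows are ± 3 days from the date of first dose". It also maps unscheduled assessments to a visit within 3 days, but only for selected vendor data.
- Section 8.2.2 multiply imputes Week 16 data that are missing without a preceding intercurrent event. Data that count as observed are not imputed.
- Section 4.2.2.1 imputes post-Baseline values in chronological order, each visit serving as a predictor for later ones.

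**The concern.** A visit label should say roughly when a measurement was taken. Under Section 3.2.2 the label of an off-schedule PEOT depends only on which visit was attended last. If the participant had attended every visit up to the PEOT, the label is at most one visit interval out. If visits were missed, nothing bounds the gap.

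The primary endpoint is exposed because a mapped lesion count is treated as observed and so displaces the multiple imputation that Section 8.2.2 would otherwise apply. A value taken weeks after Week 16 can then decide response at Week 16. In the other direction, a value taken close to Week 16 can be stored at a much earlier visit. The imputation model then treats it as an early measurement, while Week 16 is left missing.

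The intercurrent-event rule in Section 3.9 does not remove the problem. It covers systemic antibiotic rescue and stopping treatment for an adverse event or lack of efficacy. A participant who withdraws consent, for example, has no intercurrent event.

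**Working it through.** **Visit spacing.** The schedule of assessments is not in the SAP, so the spacing is derived from Section 7, which describes dosing "from Week 0 to Week 46, where 2 injections are administered at each given visit" and 48 injections in total.

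- 48 / 2 = 24 visits over Weeks 0 to 46, and 46 / 23 = 2 weeks between visits.
- Check against Section 7's own example: Weeks 0, 2, 4, 6 and 8 are 5 visits, and 5 × 2 = 10 injections, as stated there.
- Weekly visits would give 94 injections and 4-weekly visits 24, so only 2-weekly visits reproduce 48.

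The examples assume that these dosing visits are site visits with lesion counts.

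**Target days.** Study day = 7 × week + 1.

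- Week 8: 7 × 8 + 1 = Day 57
- Week 14: Day 99
- Week 16: Day 113, with a ±3-day window of Days 110 to 116

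**Applying the rule as written, with no intercurrent event**

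| Last visit with assessments | PEOT day | Filed as | Target day | Displacement |
|---|---|---|---|---|
| Week 14 | 150 | Week 16 | 113 | 150 − 113 = 37 days late |
| Week 6 | 109 | Week 8 | 57 | 109 − 57 = 52 days filed too early |
| Week 6 | 117 | Week 8 | 57 | 117 − 57 = 60 days filed too early |
| Week 14 | 100 | Week 16 | 113 | 113 − 100 = 13 days early |

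The first row has no ceiling: with Week 14 as the last visit, an off-schedule PEOT on any later date is still filed as Week 16. The last row does have one. A PEOT filed as Week 16 must follow a Week 14 visit, so it can be at most 13 days early, or 16 if the Week 14 visit was itself 3 days early.

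**Consequence for the analysis.** In rows 1 and 4 the Week 16 HiSCR50 counts as observed and is not imputed. In rows 2 and 3 Week 16 is missing, and it is imputed from a history in which a measurement made 4 days from the Week 16 target sits at Week 8.

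**The case against.** The strongest reply is that these are rare constructions. The 37-day case needs a last assessment at exactly Week 14, nothing at Weeks 16, 18 and 20, then an off-schedule PEOT, and a reason for stopping other than adverse event or lack of efficacy. Late PEOTs after stops for those two reasons are set to nonresponse whether or not data exist (Sections 3.9 and 4.2.1.1). The reference-based sensitivity analysis (Section 4.2.2.2) treats everything after treatment discontinuation as missing, so at least one planned analysis ignores these values. All of this stands. It limits how many participants are affected but does not supply the missing date limit in the primary analysis.

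Several stronger readings are tempting, and the SAP does not support them.

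- *A PEOT inside the Week 16 window is moved to an earlier visit.* A PEOT on Day 112, say, lies within Days 110 to 116. The first sentence of Section 3.2.2 most naturally leaves it unmapped.
- *All other data must fall within ±3 days.* Section 3.1 gives ±3 days as the protocol tolerance. It uses it as a mapping rule only for selected vendor data, and it does not exclude a nominal visit held outside the window.
- *Values from many weeks early can become Week 16.* With 2-weekly visits the limit is 13 to 16 days.
- *Questionnaire data are wrongly lost.* Section 3.2.2 discloses that data may land on a visit where the item is not scheduled: "Such data will not be summarized in by-visit tables (though it will be available in the listings". That is a stated choice. Its reach depends on the schedule of assessments, and the sentence concerns tables and says nothing about imputation input.
- *Stops for adverse event or lack of efficacy also escape.* After a Week 14 dose the event date is Day 99 + 17 = Day 116, so a PEOT on Days 100 to 112 precedes it. Section 4.2.3.1, however, says that a stop for lack of efficacy before Week 16 is a failure whatever the lesion count, so the point is not carried to these participants.

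**Conclusion.** The concern holds in a limited form. For participants with no intercurrent event who have missed visits, Section 3.2.2 lets a PEOT taken well after Week 16 count as the observed Week 16 HiSCR50. It also files a PEOT taken close to Week 16, but outside its window, at a visit weeks earlier. The worked displacements are 37 days late and 52 or 60 days too early. They rest on the 2-weekly visit spacing derived from Section 7.

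The SAP gives no discontinuation rate or distribution of reasons for stopping, so the number affected cannot be computed. It is probably small. Nothing here shows that the odds ratio, the power, the type I error or the primary conclusion would change, and a reader should not infer that. The case for acting is that the rule touches the primary endpoint and the imputation input and is cheap to repair.

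**What to change.** Keep the next-visit convention and add a date limit to Section 3.2.2:

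> An off-schedule PEOT is assigned to the scheduled visit, later than the last visit with assessments, whose target day is nearest the actual PEOT date. It is used as Week 16 only if it falls within ±7 days of Day 113 and before any Maintenance Treatment Period dose; otherwise Week 16 is missing and is imputed under Section 4.2.2.1. If a scheduled visit with data exists in that slot, the scheduled visit takes precedence.

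The ±7 days is half the 2-week visit interval and gives Days 106 to 120. Restricting assignment to later visits avoids the collision that plain nearest-date filing would cause: with Week 14 attended on Day 99 and a PEOT on Day 103, it would create two Week 14 records. The precedence sentence is needed because the treatment policy description in Section 4.2.1.4 allows participants to keep attending after stopping treatment. The existing antibody exception stays.

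Applied to the examples:

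- Day 150 after Week 14 goes to Week 22 (Day 155, 5 days away), and Week 16 is imputed.
- Days 109 and 117 after Week 6 become Week 16 (4 days away in each case).
- Day 100 after Week 14 is 13 days from Day 113, so it is not used, and Week 16 is imputed.

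The cost is a few lines of SAP text and a small programming change. The downside is that a few PEOT values now counted as observed at Week 16 would be imputed instead.

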3.3 Definition of Baseline values

Section 8.3.4 details the derivation of the Baseline value for the HSSDD assessment. For all other assessments, the below applies.

A Baseline value for a participant is defined as the latest non-missing measurement for that participant up to and including the day of administration of first study medication, unless otherwise stated. If a Baseline assessment is taken on the same day as first administration of study medication, it is eligible to be used as the Baseline value, even in the case that the time of the assessment is recorded as taking place after the time of first study medication administration. This is considered acceptable as this measurement is still the best representation of the Baseline value of the given assessment since it is highly unlikely that the study medication could have an impact on any measurement in such a short period of time. However, such cases should be rare as study center personnel are instructed to do all assessments at the Baseline visit prior to administering study medication. One exception to this rule is plasma concentration of bimekizumab. If Baseline plasma concentration is measured at a time after the first administration of study medication, then it will not be eligible to be considered as a Baseline plasma concentration. Such cases will be discussed with the quantitative clinical pharmacologist.

For randomized participants for whom no start date of treatment is available, the Baseline value will be considered as the last available value on or before the randomization date.

If a Baseline measurement is missing or not collected, and a Screening value is available, the Screening value will be utilized as Baseline instead.

Baseline values for component scores should be computed using components from the same visit where the relevant measurements were recorded prior to dosing. For example, if the Screening visit has all of the components, but the Baseline visit is missing 1 or more components, the Baseline value for the component score should be calculated using the Screening visit values.

When the time of first dose is derived, it will be based on the first injection of study treatment, regardless of whether or not it is an active treatment.

3.4 Protocol deviations

Important protocol deviations are deviations from the protocol that could potentially have a meaningful impact on study conduct or on the primary and key secondary efficacy, key safety, or PK outcomes for an individual participant. The criteria for identifying important protocol deviations will be defined within the appropriate protocol-specific document at study start. Important protocol deviations will be reviewed as part of the ongoing data cleaning process. Important protocol deviations including those that lead to exclusion from the analysis sets will be identified and documented prior to unblinding.

Deviations related to the Coronavirus Disease 2019 (COVID-19) global pandemic are unavoidable deviations from the protocol due to confirmed COVID-19 infection, suspected COVID-19 infection, general circumstances around COVID-19 without infection or any other deviation from the protocol due to COVID-19. COVID-19 protocol deviations will also be reviewed separately as part of the ongoing data cleaning process.

3.5 Analysis sets

3.5.1 Enrolled Set

The Enrolled Set (ES) will consist of all participants who have given informed consent.

3.5.2 Randomized Set

The Randomized Set (RS) will consist of all participants randomized into the study.

3.5.3 Safety Set

The Safety Set (SS) will consist of all participants who received at least 1 dose (full or partial) of IMP. The SS will be used for the demographic, safety, and immunogenicity analyses.

3.5.4 Full Analysis Set

The Full Analysis Set (FAS) will consist of all study participants who received at least 1 dose (full or partial) of IMP and had a valid Baseline measurement and a post-Baseline measurement for abscess, inflammatory nodules, and draining tunnel counts.

3.5.5 Active Medication Set

The Active Medication Set (AMS) will consist of all participants who have received at least 1 dose (full or partial) of bimekizumab. The AMS will be used for summaries of safety that include all data from the Initial Treatment Period and/or Maintenance Treatment Period.

3.5.6 Maintenance Set

The Maintenance Set (MS) will consist of all participants who have received at least 1 dose (full or partial) of bimekizumab in the Maintenance Treatment Period.

3.5.7 Per-Protocol Set

The Per-Protocol Set (PPS) will consist of all study participants in the FAS who had no important protocol deviations affecting the primary efficacy variable. Important protocol deviations will be predefined and study participants with important protocol deviations will be evaluated during ongoing data cleaning meetings prior to unblinding of the data.

3.5.8 Pharmacokinetics Per-Protocol Set

The Pharmacokinetics Per-Protocol Set (PK-PPS) will consist of study participants who received at least 1 full dose of bimekizumab and provided at least 1 quantifiable plasma concentration post-dose without important protocol deviations that would affect the PK.

3.5.9 COVID-19 Free Set

The COVID-19 Free Set (CFS) will consist of all study participants randomized into the study and who have no COVID-19 impact through Week 16. This analysis set will be used for sensitivity analysis of the primary efficacy endpoint.

3.6 Treatment assignment and treatment groups

It is expected that participants receive treatment as randomized and hence safety analyses will be based on the SS, as randomized. However, if after unblinding it is determined that participants randomized to placebo in the Initial Treatment Period received bimekizumab at any time within the first 16 weeks, then for safety analyses these participants will be reallocated to the appropriate bimekizumab treatment group, unless otherwise specified. Participants randomized to bimekizumab will only be reallocated to the placebo treatment group if they never received bimekizumab. Efficacy analyses will be according to randomized treatment and not actual treatment received.

For the purposes of Initial Treatment Period analyses for the [REDACTED] dosing regimen, the bimekizumab treatment arms of [REDACTED] and bimekizumab [REDACTED] treatment groups will be pooled.

